2.3.2 Known Potential Benefits

The participants will have no direct benefit from participating in the study.

The development of a host-targeted therapeutic for COVID-19 would provide significant benefits over the current standard treatment of care. COVID-19 is a highly infectious and life-threatening disease that has caused a worldwide pandemic. While vaccines have been developed to prevent the disease, they are not entirely effective, and not all individuals can receive them. As such, the availability of a host-targeted therapeutic would be critical for those who contract the disease, particularly those at high risk of severe illness or death.

The current standard treatment for COVID-19 involves supportive care, such as oxygen therapy and fluid management, and the use of antiviral drugs like Remdesivir and Paxlovid. While these treatments can manage symptoms and potentially reduce disease severity, they do not provide a cure or prevent disease progression. A host-targeted therapeutic for COVID-19 would provide a novel approach to improving the standard of care for the disease. Host-targeted therapies are

designed to target the host's cellular pathways and processes that the virus relies on for survival and replication, rather than directly targeting the virus itself. This approach has the potential to address and reduce the underlying mechanisms of COVID-19 pathogenesis and other viral disease severity (Mahajan, Choudhary et al. 2021; Dwek, Bell et al. 2022).

For example, investigators at Tulane Primate Research Center have completed two non-human primate studies in which the safety and efficacy of SLV213 were evaluated. Data from African Green monkeys inoculated with SARS-CoV-2 indicate a reduction in viral loads and a corresponding reduction in measures of lung pathology in treated animals compared to untreated controls (Frueh, Maneval et al. 2021). Histological analysis showed that treated animals were protected against ARDS-like pathology that was seen in untreated animals.

Another potential advantage of host-targeted therapies is that they could be effective against multiple strains of the virus, including emerging variants, whereas traditional antiviral therapies may only target specific strains. Additionally, host-targeted therapies could reduce the potential for the development of drug resistance, which is a concern with traditional antiviral therapies.

Host-targeted therapies could also be used in combination with other treatments, such as vaccines and antivirals, to provide a more comprehensive approach to COVID-19 treatment (Wagoner, Herring et al. 2022). For example, host-targeted therapies could be used in combination with antivirals to reduce the viral load and prevent the spread of the virus, while also targeting the host response to reduce inflammation and other damaging effects of the disease.

Furthermore, host-targeted therapies could potentially address the long-term consequences of COVID-19, such as post-acute sequelae of SARS-CoV-2 infection or "long COVID." These conditions are characterized by persistent symptoms and can have a significant impact on an individual's quality of life. Host-targeted therapies could potentially target the underlying mechanisms of these conditions and provide relief for individuals who are experiencing prolonged symptoms.

Additionally, the development of a therapeutic would help alleviate the burden on healthcare systems and resources that are currently overwhelmed by the number of COVID-19 cases. With an effective therapeutic, hospitalization rates could potentially be reduced, freeing up hospital beds and resources for those who need them most. The development of a host-targeted therapeutic for COVID-19 would be a significant advancement in the fight against this deadly disease and could save numerous lives.

2.3.3 Assessment of Potential Risks and Benefits

- Available pre-clinical and clinical data support further clinical development of SLV213. The study aim is to determine the maximum tolerated dose of SLV213 after multiple doses in order to determine a possible therapeutic dose to test in an efficacy trial.
- Risk will be minimized by housing the participants in a CTU and participants will be monitored throughout the trial by trained staff.

- Potential risks that were identified in animal studies were not evidenced in the Phase 1 clinical trial. No DLTs or SAEs were noted/occurred in the Phase 1 SAD at the highest single dose tested (800 mg). There may be other side effects or risks that are not yet known.

3. OBJECTIVES AND ENDPOINTS

OBJECTIVE	ENDPOINTS (OUTCOME MEASURES)
Primary	
Primary
 
To evaluate the safety and tolerability of multiple ascending doses SLV213 for 7 days in healthy participants.
 
Safety: Type, incidence, severity, and relatedness to study drug of all treatment-emergent systemic, laboratory and electrocardiographic (ECG) adverse events (AEs) and serious adverse events (SAEs) in each treatment cohort from the first dose (Day 1) through the last visit (Day 28 ± 2 days).
 
Tolerability: Summarized by dose cohort and include:
 
 Number (and percentage) of participants who: 
 Terminate early or are withdrawn due to treatment-emergent AEs assessed as related to intake of study medication. Have at least 1 treatment-emergent adverse event (TEAE), total and per dose level. Meet Grade 3 abnormal criteria for safety laboratory tests at least once post-dose. Meet Grade 3 abnormal criteria for vital sign measurements at least once post-dose. Meet Grade 3 criteria for safety electrocardiogram (ECG) parameters at least once post-dose. Proportion of oral medication doses completed.
Secondary	
Secondary
 
To characterize the multiple dose pharmacokinetics (PK) of SLV213 in healthy participants.
 
The following single-dose plasma PK parameters will be computed (if estimable) from the plasma total concentration-time data over the 12-hour period following the morning dose on Day 1 for each cohort:
 
 C_{max}: Observed maximum concentration T_{max}: Time of maximum concentration (h) C_{min}: Observed minimum concentration at the end of the dosing interval $AUC_{(0-t)}$: Area under the plasma concentration - time curve (AUC) to the last time with a concentration greater than or equal to the validated limit of quantitation of the assay $AUC_{(0-\infty)}$: Area under the plasma concentration-time curve to infinity $AUC_{(0-12)}$: Area under the plasma concentration - time curve from 0h (pre-dose) to 12 h after dosing

OBJECTIVE	ENDPOINTS (OUTCOME MEASURES)
	
 • $AUC_{(0-\text{last})}$: Area under the plasma concentration - time curve from time zero to the last concentration above the lower limit of quantitation • $AUC_{(0-\tau)}$: Area under the plasma concentration - time curve to the end of the dosing interval • $t_{1/2}$: Terminal half-life • CLT: Total clearance • Ke: terminal phase elimination rate constant • Vd: Volume of distribution • Dose-normalized exposure parameters ($AUC_{(0-\tau)}$/Dose and C_{\max}/Dose) 
The following multiple-dose plasma PK parameters will be computed (if estimable) from the drug total concentration-time data over the 48-hour dosing interval following the evening dose on Day 7 for each cohort.
 
 • $C_{\max,ss}$: observed maximum concentration at steady state • $C_{\min,ss}$: observed minimum concentration at the end of the dosing interval at steady state • C_{avg}: calculated average concentration during the dosing interval • $T_{\max,ss}$: Time of maximum concentration (C_{\max}) at steady state • T_{\min}: Time to minimum concentration (C_{\min}) • $AUC_{(0-48),ss}$: area under the plasma concentration - time curve from 0h (pre-dose) to 48 h after dosing at steady state • $AUC_{(0-\tau),ss}$: Area under the plasma concentration - time curve to the end of the dosing interval at steady state • $t_{1/2}$: Terminal half-life • CLT: Total clearance • Vd,ss: Volume of distribution at steady state • Linearity Index: $AUC_{(0-\tau),ss}$ (Day 7) / $AUC_{(0-\infty)}$ (Day 1) • RAUC: Accumulation ratio for AUC estimated as $AUC_{(0-\tau)}$ (Day 7) / $AUC_{(0-\tau)}$ (Day 1) • RC_{\max}: Accumulation ratio for C_{\max} estimated as C_{\max} (Day 7) / C_{\max} (Day 1). • Dose-normalized exposure parameters ($AUC_{(0-\tau)}$/Dose and C_{\max}/Dose) 
Calculate trough plasma concentrations of total SLV213 at 12h after each morning and evening dose from Day 1 through Day 7.

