- (f) Focused PE is a symptom directed PE performed as needed to assess new symptoms reported from the time of Admission on Day-1 to before the first dose, and after first dose on Day 1 to the end of the study to assess treatment-emergent AEs as needed, except on Day 9 when a complete PE is performed.
- (g) VS include blood pressure (BP), heart rate (HR), respiratory rate (RR) and temperature (T) and assessed resting supine at Screening, Day-1, within 30 min before and 2 h (\pm 10 min) after each dose on Days 1 to 7, and once daily in the morning on Day 8 and on Day 9, or ET (See [Section 8.1.1](#) and [Section 8.3.1](#). Orthostatic blood pressure and heart rate are also assessed in the standing position for 1 minute \pm 15 seconds and 3 minutes \pm 15 seconds. **NOTE: VS are taken before drawing blood for safety lab tests, plasma PK, and serum for future research if consented. Supine VS are taken before orthostatic BP and HR.**
- (h) Serum pregnancy test at Screening and Urine pregnancy test on Day-1 (See [Section 8.1.2](#)).
- (i) FSH to confirm menopause in women with amenorrhea of 12 or more months at Screening.
- (j) UDS screening for illicit drugs described in [Section 8.1.2](#) and urine alcohol test.
- (k) Urine cotinine test for nicotine use at Screening and Day-1.
- (l) HIV antibody (HIV 1 and HIV 2), Hepatitis B virus surface antigen (HBsAg) and Hepatitis C virus antibody (HCV) tests at Screening Visit (see [Section 8.1.2](#)).
- (m) SARS-CoV-2 (Covid-19) molecular diagnostic Cue Care™ test at Check-in Visit (Day-1) (see [Section 8.1.2](#)).
- (n) Clinical laboratory tests at Screening, Day-1, before the first (morning) dose on dosing Days 2, 4 and 6, and on Day 8, or ET. (See [Section 8.1.2](#) and [Section 8.3.2](#)).
- (o) UA by dipstick at Screening, Day-1, and on Days 4 and 8, or ET. If abnormal for blood, protein, glucose and nitrites, a microscopic UA will be done. The results of microscopic UA will supersede the results of dipstick UA. UA will be postponed in a menstruating female [Section 8.1.2](#) and [Section 8.3.2](#)).
- (p) 12-lead ECGs at Screening, Day-1, before the morning dose on Day 4 and at Day 8 (before the 12h PK timepoint after evening dose on Day 7), unscheduled as indicated or ET (See [Section 8.1.1](#) and [Section 8.3.1](#)).
- (q) Enrollment will occur on Day-1 after eligibility is confirmed. **NOTE: Randomization will occur before administration of the morning dose on Day 1.**

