- (r) Dose administration Q12h (\pm 15 min) for all doses following Day 1 first dose on Day 1 to Day 7. Each dose is ingested with approximately 240 mL (8 oz) or more of tap or bottled water in the fasted state. See [Section 6.2.5](#) for the duration of fast and restriction of fluid intake before and after dosing. Meals to be scheduled to accommodate dosing schedule and restrictions.
- (s) Treatment-emergent adverse events (TEAEs) and serious AEs (SAEs) will be reported and followed from the first dose (Day 1) to the last visit (Day 28 \pm 2 days). (See [Section 8.5](#) for AE and SAE definition, evaluation, and reporting.). **NOTE: Monitoring for AEs starts upon ingestion of the first capsule on Day 1.**
- (t) The interim and close-out outpatient visits on Day 15 (\pm 2 days), 21 (\pm 2 days) and 28 (\pm 2 days) may be conducted by phone to collect information about new AEs and SAEs and medication use since the previous visit. (See footnote (v) for unscheduled visits during the outpatient period)
- (u) Blood will be drawn at the following timepoints to measure the concentration of study drug and analyze PK parameters (plasma PK) and, if consented, secondary future research (serum) (See [Section 8.3.4](#)). **NOTE: Start recording time for PK collections after ingestion of the last capsule at each dose daily. Collect blood after measurement of VS and ECG recording.**

[figure not shown]
- On Day 1 MORNING DOSE: Within 30 min before the morning dose (t=0), and at 0.5h (± 5 min), 1h (± 5 min), 2h (± 5 min), 4h (± 5 min), 6h (± 10 min), 8h (± 10 min), and 12h (± 15 min) after the morning dose. (The 12h timepoint after the morning dose on Day 1 is the same as the predose timepoint before the evening dose on Day 1).
- On Day 1 EVENING DOSE: Before the evening dose (t=0), and 12h (± 15 min) after the evening dose. (The 12h timepoint after the evening dose on Day 1 is the same as the predose timepoint before the morning dose on Day 2).
- On Days 2 to 6: Within 30 min before the morning and evening doses and 12h (± 15 min) after the morning and evening doses. (The PK timepoint before each dose on Days 2 to 6 is the same as the 12h timepoint of the previously received dose.).
- On Day 7 MORNING DOSE: Within 30 min before the morning dose and at 12h (± 15 min) after the morning dose. (The 12h timepoint is the same as the predose timepoint before the evening dose on Day 7).

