4.2 Dose Escalation

Participants will be enrolled in MAD cohorts. Dosing to the next cohort will be done sequentially only after the safety assessments to Day 15 have been completed to ensure adequate time for review of all available safety and tolerability data and the safety review committee (SRC) confirms that Halting Criteria have not been met.

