8.5.9 Adverse Events of Special Interest (AESI)

Definition of AESI

An AESI (serious or non-serious) is one of scientific and medical concern specific to the compound or program, for which ongoing monitoring and rapid communication by the investigator to the Sponsor may be appropriate. Such clinically significant events may require further investigation in order to characterize and understand them and will be collected as AESIs, discussed by the SMC, and expanded narratives of each written as indicated.

Protocol-defined AESIs are:

- All clinically significant cardiovascular Grade 3 or higher AEs including symptomatic cardiac arrhythmias and ECG abnormalities
- All clinically significant Grade 3 or higher gastrointestinal AEs
- Hepatic toxicity assessed by severe (Grade 3 or higher) based on values of liver function tests (LFTs)

All AESIs will be collected through study Day 28 and will be included in the safety analysis.

All AESIs are assessed for severity and relatedness to investigational product, recorded, and followed as described above under AEs and SAEs.

Reporting of AESI

All AESIs, whether serious or non-serious, also require additional reporting to the DMID PVG within 24 hours of site awareness for serious AESI or within 72 hours of site awareness for non-serious AESI. AESIs are reported on the appropriate CRF with additional reporting to DMID PVG using the protocol-approved SAE form. Submit AESI as follows:

DMID Pharmacovigilance Group
Clinical Research Operations and Management Support (CROMS)
[name]
[name]
SAE Hot Line: [name] (US) or [name] (outside US)
SAE [contact] (US) or [name] (outside US)
SAE Email Address: [contact]

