### 4.2. Discussion of Study Design, Including the Choice of Control Groups

Given that the present study constitutes a follow-up to a completed single ascending dose (SAD) Phase 1 safety trial, a placebo control will also be utilized for the current multiple ascending dose (MAD) study. In light of this, healthy volunteers aged 18 to 65 years old will be selected in a randomized fashion to constitute a representative sample of the broader population affected by COVID-19. Due to the MAD nature of this trial, the study will allow for an assessment of safety and PK following multiple doses of SLV213 through 28 days post the first dose.

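### Laboratory and ECG events are claimed through Day 28, but the last scheduled laboratory test and ECG are on Day 8 and later testing is only event-triggered

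*Protocol*

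**What the plan says.** **Claimed window.** Protocol section 3, repeated in SAP section 3, makes the primary safety endpoint the type, incidence, severity and "relatedness to study drug of all treatment-emergent systemic, laboratory and electrocardiographic (ECG) adverse events (AEs" and SAEs, "from the first dose (Day 1) through the last visit (Day 28 ± 2 days". Protocol 8.5.9 includes an AESI worded as "Hepatic toxicity assessed by severe (Grade 3 or higher) based on values of liver function tests (LFTs" and adds: "All AESIs will be collected through study Day 28 and will be included in the safety analysis". SAP 4.2 says the design allows "an assessment of safety and PK following multiple doses of SLV213 through 28 days post the first dose". The corresponding sentence in Protocol 4.3 speaks only of multiple doses over 7 days.

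**Scheduled measurement.** Footnote (n) of the Schedule of Assessments (Protocol 1.2) places clinical laboratory tests at Screening, Day -1, "before the first (morning) dose on dosing Days 2, 4 and 6, and on Day 8, or ET". Footnote (p) places post-dose ECGs on Days 4 and 8, the second before the 12 h PK draw that follows the last dose. Vital signs, the complete physical examination and PK sampling end on Day 9. The Day 15, 21 and 28 contacts "may be conducted by phone to collect information about new AEs and SAEs and medication use since the previous visit".

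**After discharge.** Footnote (w) permits an unscheduled visit for a new adverse event of at least moderate grade, an SAE or an AESI, and for following ongoing events. Laboratory tests and an ECG are done at such a visit only as needed.

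**The concern.** Some abnormalities exist in the data only if someone takes blood or records an ECG. A hepatic AESI defined by a liver test value cannot prompt its own detection, and a symptom-free transaminase rise gives a participant nothing to report by phone. Protocol 2.3.1 names the liver as the target organ of toxicity in animals.

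The stake is how the Cohort 1 report will be read. SAP Table 22 pools adverse events, laboratory and ECG events included, over the Safety Population. SAP Table 14 counts participants with a Grade 3 laboratory or ECG result. Neither states an assessment window. Set beside a Day 28 endpoint, a zero in those rows would look like 28 days of liver and ECG surveillance. For new asymptomatic change after Day 8 it would reflect absence of measurement.

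**Working it through.** **1. Reproduce the plan's blood-volume figure, which encodes the number of safety draws.** From Protocol Appendix B, Table 3, one safety draw is 4 + 2.7 + 8.5 = 15.2 mL. Four post-dose draws (Days 2, 4, 6, 8) give 4 × 15.2 = 60.8 mL, exactly the safety-laboratory volume in Protocol 8.3.5. For the whole study, 38.9 (Screening and Day -1) + 60.8 + 30 × 6 (PK, 180) + 30 × 3.5 (stored serum, 105) = 384.7 mL, which matches the table's cumulative total at Day 9. No scheduled blood is drawn after Day 9, and no scheduled safety blood after Day 8.

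As a separate matter, the text of 8.3.5 gives PK as 160 mL and Days 1 to 9 as 325.8 mL. Then 38.9 + 325.8 = 364.7, not 384.7. The safety-laboratory figure is unaffected.

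**2. Size of the gap.** The share of the window after the last scheduled laboratory test and ECG is (end day − 8) / end day.

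| End of window | Days after Day 8 | Share |
|---|---|---|
| Day 26 | 18 | 69% |
| Day 28 | 20 | 71% |
| Day 30 | 22 | 73% |

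This is the tail after the last measurement. It is not the count of days without a test, which is 28 − 4 = 24 for laboratory tests and 28 − 2 = 26 for ECGs.

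The last dose is in the evening of Day 7. The Day 8 ECG is therefore within about 12 h of it. The hour of the Day 8 laboratory draw is not stated: about 0.5 day after the last dose if taken in the morning, up to about 1 day if later. The claimed window runs 28 − 7 = 21 days past that dose.

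**3. PK.** SAP section 10 ends sampling 48 h after the last dose, on Day 9. SAP 4.2 therefore claims 28 − 9 = 19 days with no PK sample.

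**4. What can be found after Day 8.**

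- An abnormality already present on Day 8: yes. Post-treatment abnormalities are adverse events (Protocol 8.3.3), and events are followed to resolution, stability or return to baseline (8.5.5).
- A new event the participant reports: possibly, through recall after the phone call (8.3.1) or footnote (w).
- A new asymptomatic laboratory or ECG change: not by any scheduled assessment.

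**5. Illustration with assumed rates; the documents give none.** Take 8 active participants, the planned number per cohort in SAP section 5 (SAP Table 4 shows 6). Let p be the true rate of a new Grade 3 liver test result after Day 8, and q the chance that such an event prompts an unscheduled test. The chance that at least one occurs is 1 − (1 − p)^8. The chance that at least one is observed is 1 − (1 − pq)^8.

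| p | Occurs | Observed, q = 0 | q = 0.10 | q = 0.25 | q = 0.50 |
|---|---|---|---|---|---|
| 5% | 34% | 0% | 4% | 10% | 18% |
| 10% | 57% | 0% | 8% | 18% | 34% |
| 20% | 83% | 0% | 15% | 34% | 57% |

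For asymptomatic events q is near zero, so observing none says little about whether any occurred.

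**The case against.** The strongest reply is that Day 28 is a collection window, not a measurement schedule: whatever comes to light by Day 28 counts. The plan does capture later results. Unscheduled laboratory and ECG results enter the listings and the maximum post-baseline severity (SAP 9.6 and 9.9.1), and AESIs are collected to Day 28. The animal transaminase rises were reversible, and the single-dose human study saw no clinically significant liver enzyme change (Protocol 2.3.1). All of this stands. It confines the gap to new asymptomatic change after Day 8 but does not close it.

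A reader might also infer stronger points that the documents do not support:

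- *That nothing in laboratory or ECG data can be seen after Day 8.* Event-triggered testing and follow-up of existing abnormalities are both provided for.
- *That the by-time-point tables overstate the denominator.* SAP Tables 33 to 36 and 39 use dated time points, and their N counts participants assessed at each one. Only their any-time and maximum-severity summaries lack an end day.
- *That escalation decisions rest on unmeasured data.* Protocol 4.2 allows escalation "only after the safety assessments to Day 15 have been completed", but it refers to available data and promises no laboratory test or ECG at Day 15. Cohorts 2 and 3 will not be enrolled (SAP 2.1 and 6.2), so no escalation decision remains.
- *That the endpoint should simply end on Day 8.* That could discard a genuine abnormality found at a later unscheduled visit.

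**Conclusion.** The point holds for the laboratory and ECG components of the primary endpoint and for the hepatic AESI. Their stated Day 1 to Day 28 window is one the design does not systematically observe: 20 of 28 days (71%; 69% to 73% over the ± 2-day allowance) follow the last scheduled laboratory test and ECG. The PK claim to Day 28 in SAP 4.2 conflicts with the SAP's own sampling schedule. Reported adverse events and SAEs to Day 28 are supported.

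The day counts rest only on the published schedule. The detection probabilities rest on assumed rates and serve as illustration. Nothing in the documents shows that late hepatic or ECG toxicity occurred; the point is that the planned report could not exclude it. Because the study stopped after Cohort 1, what is at stake is what the Cohort 1 report may conclude.

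**What to change.** In SAP sections 3, 4.2 and 9, by the addendum that SAP section 15 allows before final data lock, and in the CSR, state the window by component:

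- Laboratory, ECG and liver-test-defined AESI: systematically assessed to Day 8 (or early termination), then event-triggered only to Day 28, with all unscheduled results still counted.
- Vital signs, physical examination and PK: scheduled to Day 9.
- Reported adverse events and SAEs: to Day 28.

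Then:

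- Correct the SAP 4.2 sentence so that PK is not claimed to Day 28.
- Footnote the windows on pooled Tables 14 and 22, on the AESI listing (Table 28), and on the any-time and maximum-severity post-baseline summaries of Tables 33 to 36 and 39. The dated columns need no change.
- State in the CSR that absence of new asymptomatic laboratory, ECG or hepatic events after Day 8 cannot be concluded.

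If the database is already locked, the CSR alone can carry these statements. If the sponsor wants to keep the Day 28 claim for these components, the endpoint and the assessment schedule must be reconciled; no schedule is proposed here.

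The cost is a few sentences and footnotes, with no new data and no change to any analysis. The safety statement becomes somewhat more modest.
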